8.4. Data sources

The OPERA[®] (Observational Pharmaco-Epidemiology Research & Analysis) database and research network is a multi-site observational database built from the complete patient health records managed in Electronic Health Record (EHR) systems from more than 400 participating caregivers 81 separate locations throughout the U.S. (see coverage map below).

Through their membership in OPERA, medical practices meet the Centers for Medicare & Medicaid Services (CMS) Electronic Health Record (EHR) Incentive Program for Integration with a Specialized Registry. OPERA-participating physicians and ancillary healthcare providers have documented the care of over 800,000 patients in their EHRs, including 80,000 HIV+ patients of which 14.8% are women, representing 7 percent of all the HIV+ patients linked to care in the U.S. The OPERA database is refreshed from these EHR databases at each clinic on a daily basis, making the OPERA database the largest continuously operating cohort of HIV+ patients in the U.S.

In total, there are more than 2.5 million documented prospective visits in the EHR systems for these HIV+ patients and 2.6 million prescriptions written for ART medications. The average years of follow-up (years of documenting patient visits prospectively in the EHR) for patients in OPERA is 4.2 years and there are 5,479 HIV+ patients who have nine years or more of follow-up.

In addition to HIV treatment, OPERA captures the diagnosis and treatment of co-morbid conditions and diagnoses of HIV negative patients. Epividian analyses other serious co-morbid conditions such as Hepatitis C with about 8% of HIV+ patients in OPERA co-infected.

Figure 1.. U.S. Map of OPERA HIV+ Population & CDC (2010) State-by-State Estimates

8.5. Data analysis

For each time point assessed (6,12, or 24 months), the study population will be restricted to patients with a follow-up greater or equal to that time point.

8.5.1. Analysis of primary objectives

Baseline descriptive analyses of demographic and clinical characteristics

Descriptive statistics will be conducted for patients prescribed a core agent of interest between 01AUG2013 and 31DEC2017. All baseline covariates listed in sections 8.3.2. and 8.3.3. will be described, as well as baseline BMI, weight, lipodystrophy and lipid panels; medians and interquartile ranges for continuous variables and counts and percentages for categorical variables will be provided. Pairwise comparisons between DTG and each of the other core agent groups will be evaluated by p-values calculated from the Pearson Chi-Square test for categorical variables. The Fisher's exact test will be used to compare frequencies with few events. The Wilcoxon Rank Sum test will be used to calculate p-values for continuous variables.

Description of follow-up levels of total cholesterol, HDL, LDL, triglycerides, weight and BMI

Lipids (total cholesterol, HDL, LDL, triglycerides), weight and change in weight, and BMI and change in BMI will be assessed continuously and compared between patients for each core agent at 6,12, and 24 months after initiation. BMI and lipids will also be assessed categorically, as the proportion of patients in each BMI and lipid category and the proportion of patients changing categories of BMI (see section 8.3.2 for a definition of changes in categories). Given that the data reflect routine clinical care, not all patients will have the lab values of interest at each time point. The denominator for proportions will be patients tested, excluding those with missing values. Pairwise comparisons will be performed using Pearson Chi-Square test or Fisher's exact test for categorical variables and Wilcoxon Rank Sum test for continuous variables.

Description of existing lipodystrophy at core agent initiation and new diagnoses of lipodystrophy

Existing lipodystrophy will be assessed as the proportion of patients diagnosed with lipodystrophy 12 months prior to or on the index date among patients initiating each core agent of interest. New cases of lipodystrophy will be assessed as the proportion of patients who develop lipodystrophy at 6,12, or 24 months after initiation among patients without lipodystrophy at baseline. Pairwise comparisons will be performed using Pearson Chi-Square test or Fisher's exact test.

Association between type of core agent initiation and changes in BMI:

Adjusted linear regression models will be used to assess the association between core agent and mean changes in BMI at 6, 12, and 24 months. Baseline variables included in the adjusted model will be selected a priori, based on the literature, including baseline age, sex, race/ethnicity, comorbid conditions and concomitant medications associated with weight gain and weight loss [33, 34], as well as change in viral load and CD4 cell count. Factors associated with the exposure and the outcome identified in the descriptive analyses will be considered for inclusion in the adjusted model if the requirements for confounding are met. Inverse probability-of-censoring weights will be used to account for patients who discontinue treatment or are lost to follow-up and constructed using a logistic regression model.

*This analysis will be stratified by baseline BMI categories (underweight, normal weight, overweight, obese).

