8.1. Study Design

Study objectives will be evaluated through an observational analysis of a clinical cohort utilizing prospectively-collected EMR data obtained from the OPERA Observational Database. Study participants will be identified from the most recent database build available.

Period of subject inclusion:

- 01AUG2013 (DTG-approval)
- 31DEC2017

Period of observation:

- 01AUG2013 (DTG-approval)
- 31DEC2018

Population:

- A diagnosis of HIV-1, a positive HIV-1 Western Blot, or a positive HIV-1 enzymelinked immunosorbent assay (ELISA); and a detectable HIV-1 viral load test
- At least 18 years of age at the index date
- Male or female
- Prescribed one of the following core agents as part of a 3-drug regimen for the first time between 01AUG2013 and 31DEC2017:
 - DTG (Tivicay[®], Triumeq[®])
 - RPV (Edurant[®], Complera[®], Odefsey[®])
 - RAL (Isentress[®], Isentress HD[®])
 - EVG/c (Vitekta[®], Stribild[®], Genvoya[®])
 - DRV (/r/c) (Prezista[®], Prezcobix[®], Symtuza[®])
 - BIC (Biktarvy[®])
- Not exposed to >1 core agent of interest concurrently

Index date: The index date for an eligible patient is defined as the first date of the first regimen of interest ever prescribed to a patient after 01AUG2013.

Baseline period: The 12-month baseline period preceding the index date will be used to assess patient demographic and clinical characteristics. Data from the visit closest to the index date will be used for analysis.

Observation period: Patients will be observed from their index date until 6,12, and 24 months post-initiation of the regimen of interest, with the final study end date on 31DEC2018.

Censoring events: (i) End of follow-up (6,12, or 24 months after core agent initiation), (ii) cessation of continuous clinical activity*, (iii) core agent discontinuation, (iv) pregnancy, (v) death, or (vi) study end (31DEC2018).

* Continuous clinical activity is defined as at least one clinic visit within a 12month period. Patients failing to meet the continuous clinical activity requirement will be censored 12 months after their last contact.

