 - Severe dyslipidemia: ≥ 4.1 to < 4.9 mmol/L or ≥ 160 to < 190 mg/dl
 - Very severe dyslipidemia: ≥ 4.9 mmol/L or ≥ 190 mg/dl
- HDL levels¹
 - Normal: \geq 1.54 mmol/L or \geq 60 mg/dl
 - Borderline Abnormal: ≥ 1.03 to < 1.54 mmol/L or ≥ 40 to < 60 mg/dl
 - Dyslipidemia: < 1.03 mmol/L or < 40 mg/dl

¹ Cut-offs obtained https://www.nhlbi.nih.gov/files/docs/guidelines/atp3xsum.pdf

- Triglycerides levels¹
 - Normal: < 1.7 mmol/L or <150 mg/dl

 - Borderline Abnormal: \geq 1.7 to < 2.25 mmol/L or \geq 150 to < 200 mg/dl
 - Dyslipidemia: ≥ 2.25 to < 5.64 mmol/L or ≥ 200 to < 500 mg/dl
 - Severe dyslipidemia: ≥ 5.64 mmol/L or ≥ 500 mg/dl
- 3. Lipodystrophy:
 - Existing lipodystrophy: diagnosis of lipodystrophy within 12 months prior to or on index date
 - New lipodystrophy: new diagnosis of lipodystrophy at 6, 12, or 24 months after core agent initiation

A diagnosis of lipodystrophy will be identified in the EMR by searching for diagnosis codes and text consistent with lipodystrophy, lipohypertrophy, lipoaccumulation, hyperadiposity, or lipoatrophy.

Baseline	Follow-up	
Underweight (BMI: <18.5)	Underweight (BMI: <18.5)	
	Normal weight (BMI: 18.5 – 24.9)	
	Overweight (BMI: 25.0 – 29.9)	
	Obese (BMI: ≥30)	
Normal weight (BMI: 18.5 – 24.9)	Underweight (BMI: <18.5)	
	Normal weight (BMI: 18.5 – 24.9)	
	Overweight (BMI: 25.0 – 29.9)	
	Obese (BMI: ≥30)	
Overweight (BMI: 25.0 – 29.9)	Underweight (BMI: <18.5)	
	Normal weight (BMI: 18.5 – 24.9)	
	Overweight (BMI: 25.0 – 29.9)	
	Obese (BMI: ≥30)	
Obese (BMI: ≥30)	Underweight (BMI: <18.5)	
	Normal weight (BMI: 18.5 – 24.9)	
	Overweight (BMI: 25.0 – 29.9)	
	Obese (BMI: ≥30)	

Table 1. Changes in BMI categories

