8.3.3. Study covariates

The following patient demographic and clinical characteristics will be assessed when first entering the healthcare setting at one of the designated clinics or within the 12-month baseline period preceding the index date. Data from the visit closest to the index date will be used for analysis.

Demographic variables

- Age
 - Continuous (years)
 - Categorical:
 - i. 18-25 years old
 - ii. 26-49 years old
 - iii. 50+ years old
- Gender
- Race/ethnicity (Black non-Hispanic, Black Hispanic, non-Black Hispanic, American Indian, Native Hawaiian, Pacific Islander, Asian, White non-Hispanic)
- History of injection drug use (yes/no)
- Marital status (e.g., single, married/domestic partnership, widowed, divorced/separated, unknown)
- Geographic region (i.e., Northeast, Midwest, South, West)
- Payer type (i.e. Medicaid, Medicare, commercial insurance, AIDS drug assistance programs (ADAP)/Ryan White, cash, no payer information available)

Virologic variables

- HIV viral load at baseline
 - Continuous (copies/mL and log₁₀ copies/mL)
 - Categorical (naïve):
 - Low (<10,000 copies/mL)
 - Moderate (≥10,000 to <100,000 copies/mL)
 - High (≥100,000 copies/mL)
 - Missing
 - Categorical (experienced):
 - Undetectable (<50 copies/mL)
 - Suppressed (≥50 to <200 copies/mL)
 - Viremic (≥200 copies/mL)
 - Missing

Immunologic variables

- CD4 cell count at baseline
 - Continuous (cells/μL)
 - Categorical:
 - High (CD4 > 500 cells/μL)
 - Moderately High (CD4 count >350 to ≤500 cells/µL)
 - Moderate (CD4 count >200 to ≤350 cells/µL)
 - Moderately Low (CD4 count >50 to ≤200 cells/µL)
 - Low (CD4 count ≤50 cells/µL)
 - Missing

Clinical variables

- Year of ART initiation
- Length of previous regimen (ART-experienced patients only)
- Time between index and end of follow-up (months)
- AIDS defining illnesses at baseline
- Mortality Risk (VACS Mortality Index)
- Comorbid conditions occurring on or before the index date (including T2DM and thyroid disease)
- HCV and HBV co-infection
- Blood pressure
- Concomitant medications associated with weight gain [31, 32] (these medications will be characterized and considered for inclusion in the statistical adjustment set)
 - Definite:
 - i. Antipsychotics and mood stabilizers
 - chlorpromazine, clozapine, haloperidol, lithium, olanzapine, valproic acid, risperidone, quetiapine
 - ii. Antidepressants
 - phenelzine, tranylcypromine, citalopram, amitriptyline, nortriptyline, mirtazapine, paroxetine

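### Each new-lipodystrophy proportion discards diagnoses made on the core agent if the patient stops before the time point; the direction and size of any bias are unknown

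*Protocol*

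**What the plan says.** The protocol settles this outcome in four places.

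- **Estimator (Section 8.5.1).** "New cases of lipodystrophy will be assessed as the proportion of patients who develop lipodystrophy at 6,12, or 24 months after initiation". The denominator leaves out anyone who already had the condition at baseline. Agents are compared pairwise by Pearson chi-square or Fisher's exact test. Section 8.3.2 defines the event: "New lipodystrophy: new diagnosis of lipodystrophy at 6, 12, or 24 months after core agent initiation".
- **Analysis set (Section 8.5, opening sentence).** At each time point "the study population will be restricted to patients with a follow-up greater or equal to that time point". The sentence heads the whole data-analysis section and makes no exception for lipodystrophy.
- **End of follow-up (Section 8.1, censoring events).** The list includes "cessation of continuous clinical activity*, (iii) core agent discontinuation", and also pregnancy, death and study end.
- **Baseline status (Section 8.3.2).** "Existing lipodystrophy: diagnosis of lipodystrophy within 12 months prior to or on index date".

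Inverse probability-of-censoring weights for discontinuation and loss to follow-up appear in Section 8.5.1 only under the BMI-change regression. The abstract lists lipodystrophy diagnoses among the primary outcomes.

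**The concern.** BMI and lipids must be measured near the time point, so a patient who has left follow-up usually cannot contribute a value. A diagnosis is different: once recorded, it is fully observed. Requiring follow-up to reach month 6, 12 or 24 throws away events that happened on the agent before censoring.

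The outcome is tested between agents in a study meant to support evaluation of a safety signal (Section 6.2). If the link between diagnosis and stopping differs between agents, the reported proportions can differ with no true difference in risk. The protocol plans a correction for discontinuation in the BMI regression but describes none here.

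A second, smaller weakness is the risk set. Being free of lipodystrophy at baseline means no diagnosis in the preceding 12 months. Case finding is by codes and text search, so an older diagnosis mentioned again after index could register as new.

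**Working it through.** **1. Which patients the rules drop.** Follow-up ends at discontinuation (8.1), the time-point population needs follow-up at or beyond that point (8.5), and the estimator is a simple proportion in that population (8.5.1).

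| Patient | 6 months | 12 months | 24 months |
|---|---|---|---|
| Diagnosed month 3, stops month 4 | dropped | dropped | dropped |
| Diagnosed month 3, stops month 8 | can count | dropped | dropped |
| No diagnosis, stops month 4 | dropped | dropped | dropped |

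Cases and non-cases are both dropped, so what matters is whether they stop at different rates.

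**2. Size of the stopping effect.** The protocol gives no lipodystrophy rate and no discontinuation rate, so there is no figure of its own to reproduce. Every input below is an assumption. Diagnoses are taken as counted cumulatively up to the time point. Let r be the true risk by the time point, s1 the probability that a case stops before it, and s0 the same for a non-case.

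Reported proportion = r(1 − s1) / [r(1 − s1) + (1 − r)(1 − s0)]

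Example with r = 0.02, s1 = 0.50, s0 = 0.20: 0.010 / (0.010 + 0.784) = 1.26%.

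| Cases stopping (s1) | s0 = 20% | s0 = 40% |
|---|---|---|
| 10% | 2.24% | 2.97% |
| 30% | 1.75% | 2.33% |
| 50% | 1.26% | 1.67% |
| 70% | 0.76% | 1.01% |

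If s1 = s0, the factor (1 − s0) cancels and the result is r = 2.00%, with no bias. Over the grid the reported figure is 0.38 (0.76/2) to 1.49 (2.97/2, before rounding) times the true risk. It is too low when cases stop more often than non-cases and too high when they stop less often.

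**3. Effect on a comparison.** Take two agents with the same 2% risk and s0 = 20% on both. If 10% of cases stop on one and 50% on the other, the reported proportions are 2.24% and 1.26%. That is a gap of 0.98 percentage points with no true difference.

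**4. Look-back.** Let m be the share of the risk set with a diagnosis older than 12 months, q the chance that it is recorded again in follow-up and counted, and r the true risk.

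Reported = (1 − m)r + mq, so the error is m(q − r).

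With r = 1% (assumed):

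- m = 0.5%, q = 20%: error 0.005 × 0.19 = 0.095 points, reported 1.10%.
- m = 2%, q = 50%: error 0.02 × 0.49 = 0.98 points, reported 1.98%.

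The error is scaled by m. If few patients at risk have an older diagnosis it is small, even when most of those are recorded again.

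**The case against.** **The direction is not shown.** A reader might infer that diagnoses which caused patients to stop are being removed, so that drug-related harm is understated. The protocol does not support that. It links lipodystrophy to stopping nowhere, and the restriction also removes patients who stop or leave for any other reason. Equal stopping gives no bias, and lower stopping among cases gives an upward one. This objection stands in full, but it does not justify discarding observed events.

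**The objective is descriptive.** A proportion among patients followed to a fixed time is a coherent on-treatment description, and the adjusted association objective concerns BMI. That limits the consequences. It does not remove the point, because the proportions are compared between agents by significance tests on a primary outcome.

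**Re-counting is not prescribed.** A reader might also infer that old cases will be counted as new. The text asks for a new diagnosis and for patients who develop the condition, which could be programmed as first ever. What remains is that the only written exclusion is the 12-month one, and new is not tied to first ever. The contrast with "Comorbid conditions occurring on or before the index date" in Section 8.3.3 is weak support, because that section opens with first entry to care or the 12-month baseline period. Results are also stratified by ART experience, which helps show where re-recorded cases fall.

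**Survival methods are not a complete cure.** A Kaplan-Meier estimate censored at discontinuation still assumes that stopping is non-informative. This is correct, and the fix has to address it.

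**Conclusion.** The point holds in a limited form. As written, Sections 8.1, 8.5 and 8.5.1 together discard a lipodystrophy diagnosis made on the agent at every time point that the patient does not reach, and no weighting is described for this outcome. Bias follows if cases and non-cases stop at different rates. Its direction and size cannot be known from the protocol and may differ by agent. The range of 0.38 to 1.49 times the true risk rests wholly on assumed inputs.

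The look-back is a secondary point. Counting an old diagnosis as new is possible, not certain, with an error of m(q − r). The two errors can act in opposite directions. Neither affects the BMI regression. This is not a detail left to an analysis plan: the protocol itself fixes the restriction, the estimator and the baseline definition, so a plan that follows it inherits the loss of early cases.

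**What to change.** 1. Exempt lipodystrophy from the restriction in Section 8.5. Among all initiators free of prior lipodystrophy, estimate the cumulative incidence of first diagnosis from index to censoring, by Kaplan-Meier or by Aalen-Johansen with death as a competing event. Read it at 6, 12 and 24 months by agent and ART stratum (6 months only for BIC, as the protocol already provides), and base the comparison of agents on these estimates.
2. Because this still assumes non-informative censoring at discontinuation, either apply the censoring weights already planned for BMI or add a sensitivity analysis with discontinuation as a competing event. The latter estimates the probability of a diagnosis while still on the agent and should be labelled so.
3. Exclude from the risk set any patient with lipodystrophy recorded on or before index, using all available history, and define a new case as the first recorded diagnosis.

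The cost is a change of protocol wording and standard procedures on the same data. The longer look-back leaves slightly fewer patients at risk and makes look-back length unequal between patients, so its distribution by agent should be reported.

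### Patients come from 81 locations, but no clinic variable, clinic term or clustered variance is named, so clinic differences could be read as core-agent effects if agent choice and BMI change both vary by clinic

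*Protocol*

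**What the plan says.** Section 8.4 says that OPERA "is a multi-site observational database built from the complete patient health records", contributed by "more than 400 participating caregivers 81 separate locations throughout the U.S". Section 9 adds that each clinic first has its own database, and that these are then de-identified and pooled.

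For the second primary objective, section 8.5.1 states: "Adjusted linear regression models will be used to assess the association between core agent and mean changes in BMI". The fit uses inverse probability-of-censoring weights and is stratified by baseline BMI category. The adjustment set is described as "including baseline age, sex, race/ethnicity, comorbid conditions and concomitant medications associated with weight gain and weight loss", together with change in viral load and CD4 count. Other variables can enter by this route: "Factors associated with the exposure and the outcome identified in the descriptive analyses will be considered for inclusion in the adjusted model". No variance estimator is stated.

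The only place variable in section 8.3.3 is "Geographic region (i.e., Northeast, Midwest, South, West". Clinic and prescriber are not listed.

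For the descriptive objective, agents are compared by unstratified tests. For lipodystrophy the text reads: "Pairwise comparisons will be performed using Pearson Chi-Square test or Fisher's exact test". Continuous outcomes use the Wilcoxon rank sum test. Section 8.5.3 and Table 2 size the regression without mentioning clinics.

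**The concern.** Prescribers choose the core agent, and clinics weigh patients and code lipodystrophy. Patients at one clinic may therefore resemble each other in both exposure and outcome. Two separate consequences follow if they do.

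- **Precision.** A test that assumes independent patients understates the standard error of an agent contrast.
- **Confounding.** If clinics that favour one agent also see larger BMI gains for other reasons, the unadjusted clinic difference moves into the agent coefficient. A clustered variance alone does not cure this; a within-clinic comparison does. Four regions are too coarse to stand in for 81 locations.

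The study is meant to support a safety-signal evaluation (section 6.2), and the expected differences between agents are small, so modest clinic effects could matter. Lipodystrophy is the most exposed outcome: section 8.3.2 finds it by searching codes and text, which depend on local habit, and it is compared without any adjustment.

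**Working it through.** **1. Does Table 2 allow for clinics?** Inputs from section 8.5.3: 4 exposure degrees of freedom, 10 covariates, 80% power. Alpha is not stated; 0.05 is assumed. The calculation is a noncentral F test with 4 and N − 4 − 10 − 1 = N − 15 degrees of freedom and noncentrality N·ρ²/(1 − ρ²). The smallest N reaching 80% power matches all ten rows exactly. For example, at ρ = 0.20, power is 0.7994 for N = 291 and 0.8009 for N = 292 (Table 2: 292). At ρ = 0.12, it is 0.7996 for 821 and 0.8002 for 822 (Table 2: 822). The table therefore contains no design effect.

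**2. Inflation for an agent contrast.** The agent varies within clinics, so the variance inflation is

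D = 1 + (m − 1) × ICC_outcome × ICC_agent,

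with m patients per clinic. The true standard error is √D times the naive one, and the real type I error of a nominal 5% test is 2[1 − Φ(1.96/√D)]. Here m is N/81, with equal clinic sizes and the section 8.5.3 counts. Both ICCs are assumptions: outcome 0.01 to 0.05, agent choice 0 to 0.20.

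| Group | N | m | Largest D | Largest √D | Type I error range |
|---|---|---|---|---|---|
| Underweight | 510 | 6.3 | 1.05 | 1.03 | 5.0% to 5.6% |
| Normal weight | 6,598 | 81.5 | 1.81 | 1.34 | 5.0% to 14.5% |
| Overweight | 6,298 | 77.8 | 1.77 | 1.33 | 5.0% to 14.0% |
| Obese | 3,964 | 48.9 | 1.48 | 1.22 | 5.0% to 10.7% |
| All, unstratified | 17,370 | 214.4 | 3.13 | 1.77 | 5.0% to 26.8% |

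Example, normal weight at the upper end: D = 1 + 80.5 × 0.05 × 0.20 = 1.81 and √D = 1.34, giving 14.5%. A middle case (0.02 and 0.10) gives D = 1 + 80.5 × 0.002 = 1.16 and 6.9%. If the agent mix is the same everywhere, ICC_agent = 0 and D = 1.

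**3. Check by simulation.** Setting: 81 clinics, N = 6,598, a two-agent contrast, no true effect, 600 runs per setting. In the middle case the rejection rate was 0.075 with equal and 0.098 with unequal clinic sizes (Monte Carlo error about 0.01). With equal agent mix across clinics it was 0.037 to 0.063. A clinic fixed effect returned it to about 0.04 to 0.07 in every setting.

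**4. Confounding, illustrated.** Let clinic agent preference and clinic BMI trend correlate at r. For a binary agent with equal groups (SD 0.5), the bias in outcome SD units is r × √(ICC_outcome × ICC_agent)/0.5. With r = 0.3 (assumed) and the middle case, this is 0.3 × √0.002/0.5 = 0.027. Simulation gave about 0.026 and a type I error of 0.20 to 0.23; a clinic fixed effect returned it to 0.04 to 0.055.

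To put this in BMI units, section 6.1 cites a cohort with six-month gains of 0.18 ± 0.08 on DTG (n = 225), 0.17 on RAL and 0.21 on EVG. If ± is a standard error (RPV: 0.06/0.07 = 0.86, which fits its p = 0.39), the DTG SD is 0.08 × √225 = 1.2. The bias is then 0.026 × 1.2 = 0.03 kg/m². The cited differences from DTG are 0.01 (RAL) and 0.03 (EVG).

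**The case against.** The strongest reply is that the protocol is silent on the regression's variance rather than wrong about it. A separate analysis plan, not at hand, could set clinic-clustered errors or a clinic effect. That stands: a reader might infer that the BMI model is fixed as assuming independence, and the text does not say so. It does not rescue the named pairwise tests, Table 2, or a covariate list written out in detail without clinic.

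A reader might also infer that clinic can never enter the model. That is too strong. The a priori set is introduced as an inclusion list and is not closed. However, extra factors must be identified in the descriptive analyses, and those are specified for the listed variables, so clinic would be examined only if someone added it.

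The size of the harm is open to challenge too. The ICCs are assumed, the counts are baseline counts before the follow-up restriction and measurement windows, and a pairwise contrast uses only part of each stratum. The 81 locations describe the whole database, so the number contributing to this cohort is unknown. The calculations carry no covariates. Unequal clinic sizes work the other way. These points all stand, and they are why only ranges are given.

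Finally, objective 1 is descriptive and its tests adjust for nothing, so rewriting all of them is largely optional. That stands as well.

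**Conclusion.** The gap is real, and closing it is a cheap improvement. For data from 81 locations, the protocol names no clinic variable, no within-clinic comparison and no clustered variance, and its pairwise tests and sample-size table treat patients as independent.

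The consequence is conditional on both agent choice and outcome varying by clinic. Under the assumed ICCs, the real type I error is about 5% to 15% in the normal-weight stratum and about 5% to 6% in the underweight stratum. The figure of up to about 27% applies only to tests in the unstratified 17,370. It should not be read as the error rate of the BMI-change model, which is stratified by baseline BMI. Nor do the documents support saying that standard errors are certainly too small: the protocol gives neither ICC, and a similar agent mix across clinics would leave essentially no inflation. The confounding example shows that a bias as large as the cited differences between DTG and other integrase inhibitors is possible, not that it is present.

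**What to change.** - **Section 8.3.3:** add a de-identified clinic code. Section 9 describes separate clinic databases, so one should be obtainable.
- **Section 8.5.1, BMI-change model:** include clinic as a fixed effect. Where clinics are small, as in the underweight stratum (510/81, about 6 per location), pool small clinics or use a random intercept plus the clinic-level agent proportions, so that the agent contrast is within clinic. A random intercept alone is not enough. In a simulation with N about 510, outcome ICC 0.05 and a correlation of 0.5 between clinic preference and outcome, bias was 0.068 SD unadjusted, 0.054 with a random intercept and about 0 with fixed effects.
- **Section 8.5.1, variance:** compute standard errors clustered by clinic around the censoring-weighted fit.
- **Objective 1 comparisons:** at least for lipodystrophy, use clinic-stratified or clinic-clustered tests, or present the results without p-values.
- **Section 8.5.3:** state that Table 2 assumes independent patients.

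The cost is a few sentences and little programming. Intervals will be somewhat wider, and some small clinics will need pooling.
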